We propose to test BUP microdosing vs. treatment as usual (TAU), meaning standard BUP induction. We will conduct a hybrid type 1 effectiveness-implementation study, using a pragmatic, open-label, randomized controlled trial (RCT). We will randomize 270 hospitalized patients with (a) CP and (b) opioid misuse or OUD to a 4-day microdosing protocol (without stopping full agonists) or 2-day standard induction (with stopping full agonists), and link them to outpatient BUP treatment. Study assessment visits will occur at baseline, 1 week, and 1, 3, and 6 months. The primary outcome will be BUP treatment uptake (taking BUP 7 days after baseline). Secondary OUD outcomes will be illicit opioid use and retention in care at 1, 3, and 6 months. Secondary pain outcomes will be pain intensity, pain interference, and quality of life at 3 months. Changes in pain and quality of life will be mediated by BUP treatment uptake and retention. During induction and 3-months of follow-up, we will also collect data for Ecological Momentary Assessment (EMA) of opioid withdrawal, craving, pain, and anxiety ("opioid- and pain-related symptoms"). These EMA data will allow us to assess whether BUP microdosing's targets of engagement—opioid- and pain-related symptoms—mediate OUD outcomes. Exploratory analyses will also examine pain as a trigger for opioid relapse.

Aim 1: To test the effectiveness of microdosing (vs. TAU) on OUD outcomes.

***H₁:* The microdosing arm (vs. TAU) will have better BUP treatment uptake and retention, and less illicit opioid use. *H₂:* Improvements in H₁ will be mediated by opioid- and pain-related symptoms.**

Aim 2: To test the effectiveness of microdosing (vs. TAU) on pain outcomes.

***H₃:* The microdosing arm (vs. TAU) will have less pain intensity and interference, and improved quality of life. *H₄:* Improvements in H₃ will be mediated by OUD outcomes.**

Aim 3: To inform future implementation and dissemination efforts, we will: 3a) Examine factors influencing reach, adoption, implementation, and maintenance of BUP microdosing. We will use qualitative and quantitative methods to describe multi-level factors influencing these domains; **3b) Calculate**

the cost and examine cost-effectiveness of BUP microdosing. H_5 : Compared with TAU, BUP microdosing will be cost-effective from a societal and a health sector perspective.

[figure not shown]
B. SIGNIFICANCE

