Study logs: We will use study logs to examine the number of potential participants screened, consented, and reasons for declining consent. Study clinicians will document the amount of time that they spend during BUP induction using the microdosing or TAU protocol following a check-list of steps.

Ecological momentary assessment (EMA): We will use EMA to examine opioid and pain-related symptoms (opioid withdrawal and craving, pain, anxiety), along with illicit opioid use, BUP dose taken, and pain treatments. Using smartphone mobile technology, participants will receive time-scheduled prompts to report symptoms, ecological conditions (e.g., current activities), and behaviors. We will record assessments in two periods: the first 2 weeks (induction) and 3-month follow-up. During induction, participants will report opioid- and pain-related symptoms at random times during 5 daily blocks. The relatively long period of data collection oriented to induction will allow EMA data collection in the hospital and after participants return home to resume normal activities. During follow-up, we will collect data during three additional 1-week “bursts” to complement data from in-person study visits. Bursts will be separated by at least 2 weeks and no more than 6 weeks over 3 months. Prompts will inquire about opioid- and pain-related symptoms, and context, such as physical activity, which may affect these symptoms and OUD or pain outcomes. As with our current studies, research staff will assist in downloading the secure customized EMA technology (www.llumivu.com) onto participant smart phones, and provide training to use the technology.¹⁰⁶ Participants without smart phones will be provided one. Each report will take 1-2 minutes to complete. Based on the lack of significant reactivity effects found in past research, 5 standard EMA random reports will be prompted daily.^{117,118} EMA measures are summarized in **Table E-4**.

Adherence to EMA: Participants will receive \$0.20 for each set of assessments completed. If they complete more than 90% of assessments weekly, they will receive a bonus of \$10. Feedback regarding EMA adherence will be provided with reminders about compensation. Total compensation can be \$17 per EMA week.

E.2.10 Key Outcomes for Aims 1 and 2:

The **primary outcome** will be **BUP uptake**, defined as receiving BUP 7 days after the baseline visit using EHR data on hospital medication administration or prescription (dichotomous, yes/no).

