Sex as a biological variable. For Aims 1 and 2, we will examine sex as a biological variable by conducting stratified analyses by sex. In addition, we will conduct exploratory analyses to test whether there is a two-way interaction between OUD and pain outcomes and sex.

Exploratory analysis: E₁: During induction, opioid withdrawal and pain will be lower in the microdosing (vs. TAU) arm. We will use EMA data (5 random reports per day: within-individuals, repeated data) to examine if those in the microdosing arm report less opioid withdrawal and pain. Multilevel models will be used where random reports that record changes in opioid withdrawal and pain are assessed within individuals (level 1), and study arm is assessed between individuals (level 2). For example, study arm (level 2: microdosing vs. TAU) will be regressed onto opioid withdrawal (level 1). A significant coefficient for study arm indicates significant differences in overall levels of opioid withdrawal across study arms. We will also describe daily changes (linear or curvilinear) in opioid withdrawal and pain over time by including time (days since the beginning of induction) in the models above. Subsequently, a treatment x time interaction term will be included in models to examine if the trajectory (rates of changes over time) of opioid withdrawal and pain differ across study arms. Separate models will examine opioid withdrawal and pain, and separate models will examine induction (weeks 1, 2) and follow-up (1, 2, 3 months).

E₂: Increases in pain intensity will be associated with illicit opioid use in follow-up. We will use EMA data (5 random reports per day: the within-individuals, repeated data) to examine whether increases in pain are associated with illicit opioid use during the follow-up period (three 1-week bursts). We will use multilevel models to prospectively examine whether pain level at time 1 (T1) predicts illicit self-reported opioid use between T1 & T2, controlling for the previous pain level (T0), age, sex, and use of other pain treatments. In addition, we will include a pain x BUP initiation interaction term to test whether the relationships between pain and subsequent illicit opioid use differ across participants who do and do not initiate BUP treatment.

D.2.12 Power and Sample Size: We will power the study based on the primary outcome of BUP uptake. We plan to enroll 135 participants in each arm. While published case studies report high levels of success with

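### E2 asks whether a rise in a participant's own pain precedes opioid use, but its model uses pain levels with no within/between split and omits use in the preceding interval, so the answer can be biased in either direction

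*Combined protocol and SAP*

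**What the plan says.** Section D.2.11 gives E2 as the hypothesis "Increases in pain intensity will be associated with illicit opioid use in follow-up". Section A announces the same question: "Exploratory analyses will also examine pain as a trigger for opioid relapse".

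The covariates are given in one closed list, "controlling for the previous pain level (T0), age, sex, and use of other pain treatments". The predictor is a score at a single prompt and the outcome is use in the interval that follows: the question is put as whether "pain level at time 1 (T1) predicts illicit self-reported opioid use between T1 & T2". A further term is planned for the same model: "we will include a pain x BUP initiation interaction term". Its purpose is to compare the relation in those who start BUP with that in those who do not.

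The data are the follow-up EMA reports. Section D.2.9 says "5 standard EMA random reports will be prompted daily", and there are three one-week bursts, so a participant gives at most 3 × 7 × 5 = 105 reports. The same section and Table E-4 show that EMA also collects self-reported illicit opioid use.

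E2 does not state the link function, the random effects, any centring of pain, or how overnight and between-burst gaps are treated. It calls the EMA data repeated measurements within individuals. It does not assign pain to a level, whereas E1 places symptoms at level 1 and study arm at level 2.

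**The concern.** The hypothesis concerns change within a person; the stated predictor is a level. Two paths can then reach the T1 coefficient without pain being a trigger.

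- **Between persons.** If participants with higher average pain also have a higher propensity to use, a raw T1 score carries part of that difference. A random intercept does not remove it, because the model takes the intercept to be independent of the predictors.
- **Prior use.** If use between T0 and T1 makes use between T1 and T2 more likely and also moves the T1 pain score, it confounds T1 pain with the outcome. If use raises pain, the bias is towards a trigger. If use lowers pain, the bias hides a trigger or reverses its sign.

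The protocol's own background makes both paths plausible. Section B.1 says that many people misuse prescription opioids to control pain and that full agonists can worsen pain through hyperalgesia. Section B.7 cites a trial in which high and fluctuating pain went with later relapse.

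B.7 also cites studies that found no association between pain and use. E2 would therefore be read as evidence on an open question, and as stated it could not separate a trigger from these two alternatives.

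**Working it through.** E2 states no power, error rate or effect size, so there is no figure of its own to reproduce. The check is a simulation of the E2 design.

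**Models** (use taken as yes/no per interval, random intercept a_i for participant i):

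- As stated: logit P(use in T1–T2) = a_i + b1·pain(T1) + b0·pain(T0).
- Corrected: logit P(use in T1–T2) = a_i + b1·[pain(T1) − m_i] + b0·[pain(T0) − m_i] + g·m_i + c·use(T0–T1), where m_i is the participant's mean pain.

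Age, sex and pain treatments were left out because they played no part in generating the data.

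**Inputs from the documents.** 135 per arm, so 270 (D.2.12); 84% retention in earlier research (D.2.6), so 0.84 × 270 = 227 participants; five reports a day over three one-week bursts.

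**Assumptions not in the documents.** 80% of prompts answered independently; within-day T0–T1–T2 triples only; use in about 12–15% of intervals; SD of pain 1.4 between and 1.2 within persons, autocorrelation 0.5; random-intercept SD 1.2. The two SDs give a total of √(1.96 + 1.44) = 1.84, somewhat above the baseline SD of 1.6 in D.2.12.

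**Rows.** Five reports a day give 3 triples, and 3 × 21 days = 63. With 0.8³ = 0.512 complete, that is about 32 rows each and 227 × 63 × 0.512 ≈ 7,320 in all.

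**Varied.** Correlation r of mean pain with propensity to use; carry-over of use to the next interval (log-odds); effect of use on the next pain score; true within-person effect (log-odds per point).

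Results from 300 simulated trials per row, two-sided 5% tests. The percentage is the share with a significant positive T1 term (nominal 2.5% when the true effect is zero); the mean estimate follows in brackets.

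| True effect | Scenario | As stated | Corrected |
|---|---|---|---|
| 0 | no links | 2.3% (0.003) | 2.7% (0.002) |
| 0 | carry-over 1.0, use does not move pain | 4.0% (0.002) | 2.7% (0.002) |
| 0 | r = 0.3 only | 15.0% (0.036) | 2.0% (0.002) |
| 0 | r = 0.5 only | 37.0% (0.061) | 3.7% (0.002) |
| 0 | carry-over 1.0, use raises pain 0.5 | 49.7% (0.068) | 0.7% (−0.012) |
| 0 | the same, with r = 0.3 | 78.0% (0.097) | 1.3% (−0.012) |
| 0 | carry-over 1.0, use lowers pain 0.5 | 0%; 47.3% significantly negative (−0.064) | 7.0% (0.016) |
| 0.10 | no links | 67.7% (0.089) | 78.0% (0.101) |
| 0.10 | carry-over 1.0, use lowers pain 0.5 | 8.0% (0.021) | 87.3% (0.114) |
| 0.10 | carry-over 1.0, use lowers pain 1 | 0.7%; 15.0% significantly negative (−0.030) | 95.7% (0.128) |

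**Each change alone.**

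- Adding only the person mean leaves 42.3% false triggers when use raises pain by 0.5.
- Adding only prior use leaves 15.7% at r = 0.3 and 37.0% at r = 0.5.
- In the masked case (true 0.10, use lowers pain 0.5), power is 8.0% as stated, 15.0% with the person mean only and 75.0% with prior use only. The masking therefore comes mainly from the omitted prior use.

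**Precision.** One standard error is at most √(0.5 × 0.5 / 300) = 2.9 percentage points.

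A separate, smaller simulation (60 trials per case, standard error up to √(0.25 / 60) = 6.5 points) agreed. As stated, the model gave 0–2% false triggers with the links absent, 12% under a modest between-person link, 38% when use carried over and raised pain by 0.5, and 2% power for a true 0.10 when use relieved pain. With both changes the last three became 0%, 0% and 85%.

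**The case against.** The strongest reply is that E2 already contains protection. The outcome follows the predictor in time, the model is multilevel, and with T0 pain included the T1 coefficient is the effect of change given prior pain. This stands in part: T0 absorbs some of the between-person link. Every figure above for the model as stated includes the T0 adjustment, however, so it does not remove the bias.

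Second, the plan never says pain will be left uncentred. That is right. A reader might infer a deliberate choice of raw scores, but the text is only silent. The omission of T0–T1 use is different, because the covariates are listed and it is not among them.

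Third, a reader might infer that E2 would usually give a false answer. The documents do not support that. They give no value for the between-person link, the persistence of use or its effect on pain, and with those paths absent the error stays near nominal. The studies cited in B.7 with no association also argue against taking a strong link for granted.

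Fourth, B.7's heading might suggest that the follow-up bursts exist for E2. Section D.2.9 says they complement the in-person visits, and EMA data also serve the mediation analyses and E1.

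Finally, lack of a split does little to hide a real effect: 67.7% against 77.3% power with the person mean added and no other links. That is correct.

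**Conclusion.** The point holds conditionally. E2 poses a within-person question but specifies pain levels, no within/between separation and no adjustment for use in T0–T1. Following it as written can produce a spurious trigger or conceal a real one, depending on links that the protocol's background makes plausible but does not quantify.

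Under the assumed values and taking both simulations together, the false positive trigger rate is about 2–4% with the paths absent, 12–37% with a between-person link only, 38–50% when use carries over at 1.0 log-odds and raises pain by 0.5 point, and about 78% with both. Power for a true 0.10 log-odds per point is about 2–8% when use carries over and lowers pain by 0.5 point, against about 85–87% with both changes. These figures show the possible range; they do not predict this trial's error rate.

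E2 is exploratory and carries no power or error claim. The primary outcome, the secondary outcomes and the sample size are untouched.

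**What to change.** In D.2.11, rewrite the E2 model as follows:

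- enter each participant's mean pain at level 2 and the deviations from that mean at T1 and T0 at level 1;
- add self-reported illicit opioid use in T0–T1 to the covariates;
- read E2 from the T1 deviation term;
- build the interaction with BUP initiation on that same term;
- state the link, the random effects, and how overnight and between-burst gaps are handled.

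This changes analysis wording only, since EMA already collects every variable. There are two costs. Some rows are lost where the prior report is missing. Also, a lagged outcome beside a random intercept, in a model that carries a person mean from the same reports, leaves a small bias: mean estimates of −0.012 to 0.016 when the truth is zero, 0.101 to 0.128 when it is 0.10, and up to 7.0% false positive triggers. The model without lagged use should therefore be reported as a sensitivity analysis.

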Secondary OUD outcomes include illicit opioid use and BUP retention. **Illicit opioid use** will be examined as the number of days of illicit opioid use (defined as self-reported use of heroin, fentanyl, or non-prescribed opioid analgesics) in the prior 30 days based on the Addiction Severity Index (continuous).¹¹⁹ Because urine drug testing (UDT) only captures opioid use in the prior 24-72 hours, it is a less sensitive measure of substance use over time; however, UDT results will be a secondary outcome measure. **BUP retention** will be

Table E-4. Ecological Momentary Assessment (EMA) Measures

Construct	Measure
EMA opioid- and pain-related symptoms	
Opioid withdrawal	Subjective Opioid Withdrawal Scale (SOWS)
Opioid craving	Visual analog scale
Pain intensity	Adapted BPI pain severity subscale
Anxiety	Generalized Anxiety Disorder-7 (GAD-7)
Exploratory EMA outcomes	
Illicit opioid use	Self-report
BUP dose	Self-report
Pain treatment	Self-report

*All measures will occur at bursts 1 & 2 weeks, and 1, 2, & 3 months

defined as having a BUP prescription written the following number of days after baseline: 30-60 days (1-month retention); 90-120 days (3-month retention); and 180-210 days (6-month retention). To be retained at 3 and 6-months, participants will be required to have been retained at previous time points.⁴⁶ All OUD outcomes are consistent with elements of the Opioid Use Disorder Cascade of Care.¹²⁰

Secondary pain outcomes include pain intensity, pain interference, and quality of life. *Pain intensity* will be measured using the Brief Pain Inventory (BPI).¹²¹ We will use the mean of 4 items that assess pain intensity over the past 24 hours on a scale of 1-10 (1=minimal pain, 10=intense pain). We will use the mean of these 4 items. *Pain interference* will be measured using the pain interference scale from the BPI, which is a 7-item instrument measuring the impact of pain on daily activities and physical functioning. It is rated on a scale of 1-10 (1=minimal interference, 10=high interference). We will use the mean of these 7 items. *Quality of life* will be measured using the PROMIS-Preference Scoring System (PROP-Pr), which is described in detail as part of the cost-effectiveness analyses below (see D.4.1).¹²²⁻¹²⁴ In our main analyses, we will examine changes from baseline to 3 months for all pain outcomes; in additional analyses, we will examine sustainability at 6 months.

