microdosing (nearly 100%), we will use a more conservative estimate of treatment uptake from our experience with microdosing (61%). In a controlled trial of standard induction to transition patients with CP from full opioid agonists to BUP, only 24% were successful with BUP uptake.⁵⁸ To detect a difference of this size in BUP uptake, we would only need 27 participants in each arm to assure 80% power. However, we will recruit a larger sample to account for the possibility that uptake will be greater than 24% in the TAU arm (see **Table E-5**). Even with study attrition, we will be

able to assess BUP uptake for all participants based on medical record extraction,

For pain outcomes, we based our power calculations on expected changes in pain intensity from baseline to 3 months. Our pilot data (see D.1.1) suggests that mean (SD) pain intensity score will be 7.3 (± 1.6) at baseline for all participants. With a sample of 270 participants (135 per arm), the minimum effect size (Cohen's d) that can be detected with power of 80% is 0.34. This effect size corresponds to a difference between arms (microdosing vs. TAU) of 8.4% for participants'

reduction in pain scores (assuming that the SD of change is 1.8). Note that the SD for the pain score change is greater than that of the pain intensity score at each time point due to the intra-participant correlation in pain intensity over time. Because pain reduction is only considered for participants with BUP uptake, attrition is already incorporated into these estimates.

D.3 Aim 3a) Examine factors influencing reach, adoption, implementation, and maintenance of the microdosing protocol.

D.3.1 Overview and hypotheses. In this hybrid type 1 effectiveness-implementation trial, we will use RE-AIM and CFIR frameworks to guide Aim 3a, in which we will use qualitative and quantitative methods to describe multi-level factors influencing reach, adoption, implementation, and maintenance of BUP microdosing.

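### The main pain contrast is not pinned down or baseline-adjusted; on the plan's own SD statement a change score is the least precise option, and the reason given for its larger SD is backwards

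*Combined protocol and SAP*

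**What the plan says.** E.2.10, on the secondary pain outcomes, says of the main analyses that "we will examine changes from baseline to 3 months for all pain outcomes"; 6 months is left to additional analyses.

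D.2.12 powers pain on the same quantity. It takes from the pilot that "mean (SD) pain intensity score will be 7.3 (± 1.6) at baseline for all participants". With 135 per arm it states that "the minimum effect size (Cohen's d) that can be detected with power of 80% is 0.34", and converts this to 8.4%, "assuming that the SD of change is 1.8". It then remarks that "the SD for the pain score change is greater than that of the pain intensity score at each time point", and puts the excess down to correlation between a participant's own scores. It gives neither the 3-month SD nor the significance level.

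H3 in D.2.11 describes the model: a separate linear mixed model for each pain outcome, using in-person data from baseline, week 1, month 1 and month 3. Arm is fixed; participant and time are random. It states no arm-by-time term, no equal-baseline constraint and no baseline pain covariate. Covariates enter only in additional analyses. The baseline pain score is absent both from the covariate list in E.2.10 and from the confounders named in D.2.11. Table E-3 schedules BPI severity, BPI interference and PROPr at baseline.

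**The concern.** Two things look wrong. First, the explanation for the SD of change has the sign of the correlation reversed. Once the sign is put right, the plan's own SDs describe a setting of weak correlation, in which subtracting the baseline adds more noise than it removes.

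Second, three sections bear on one comparison and do not fix it. E.2.10 and D.2.12 point to change at 3 months. H3, read literally, yields a single arm effect across visits that include one before treatment. The choices that determine what H3 estimates, and how precisely, are left open.

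Pain is the whole of Aim 2, and its outcomes are the dependent variables in the H4 mediation models. What is at stake is precision that a baseline score already collected could supply, and a contrast settled before data are seen.

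**Working it through.** **Inputs.** From D.2.12: baseline mean 7.3 and SD 1.6, SD of change 1.8, 135 per arm, 80% power. Assumed: two-sided 5%, which reproduces the stated d (one-sided 5% would give 0.30). The 3-month SD, s3, is not stated; D.2.12 implies only that it is below 1.8. All 270 participants contribute unless noted.

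**The plan's figure.** d = (1.960 + 0.842) × √(2/135) = 0.341. Then 0.34 × 1.8 = 0.612 points, and 0.612/7.3 = 8.4%. Both stated figures reproduce for a change score.

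**Direction of the correlation effect.** Var(change) = s0² + s3² − 2ρ·s0·s3, so a larger ρ gives a smaller SD of change. With SD 1.6 at both times the SD of change is 2.26 at ρ = 0, 1.80 at 0.37, 1.60 at 0.5 and 1.24 at 0.7. With equal SDs it exceeds 1.6 only when ρ is below 0.5.

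**Implied correlation and precision.** ρ = (1.6² + s3² − 1.8²)/(2 × 1.6 × s3). Baseline-adjusted SD = s3 × √(1 − ρ²). Sample ratio, change against adjusted = (1.8/adjusted SD)². Adjusted detectable difference = 0.341 × adjusted SD.

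| 3-month SD | ρ | Adjusted SD | Sample ratio | Adjusted detectable difference |
|---|---|---|---|---|
| 1.2 | 0.20 | 1.176 | 2.34 | 0.40 (5.5%) |
| 1.4 | 0.29 | 1.342 | 1.80 | 0.46 (6.3%) |
| 1.6 | 0.37 | 1.488 | 1.46 | 0.51 (7.0%) |
| 1.8 (limit) | 0.44 | 1.612 | 1.25 | 0.55 (7.5%) |

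The change-score SD is 1.8 in every row. It therefore exceeds the 3-month SD wherever D.2.12's statement holds, and the adjusted SD is never above the 3-month SD. At a 3-month SD of 1.6, the detectable differences are 0.61 (8.4%) for change, 0.55 (7.5%) for the 3-month score alone and 0.51 (7.0%) adjusted.

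**With dropout.** D.2.6 cites 84% retention at 6 months in earlier work: 0.84 × 135 ≈ 113 per arm, and 2.802 × √(2/113) = 0.373. Adjusted: 0.373 × 1.488 = 0.55 points (7.6%). Change: 0.373 × 1.8 = 0.67 points (9.2%).

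**What the H3 model estimates.**
- Arm main effect only, as written. If the four visits are weighted equally, an effect constant over the three follow-up visits is reported at three quarters of its size (0.612 becomes 0.459). This is neither the change nor the 3-month difference.
- Arm-by-time term, free baseline means, unstructured covariance, complete data. The 3-month contrast equals the change-score estimate.
- Arm-by-time term with a common baseline mean. Precision is about that of adjusting for baseline.

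**The case against.** The strongest reply is that the analysis section does not plan a change-score test. H3 is a longitudinal mixed model, and the wording in E.2.10 is compatible with one. This stands. A reader might infer that 135 per arm will do the work of about 92 (135/1.46). The documents do not support that as a statement about the planned analysis: it describes the power formula, or one implementation of H3, at one assumed 3-month SD. The literal H3 model need not even be weak. With equal correlation of 0.37 between visits and a constant 0.612-point effect, its power is about 90%, against 80% for change and 92% for the adjusted 3-month score. Its fault is what it estimates. The reply does not rescue the plan, because nothing in H3 commits to the efficient version.

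It is also fair that ρ = 0.37 is not a figure in the plan. Only the bound of about 0.44 follows from D.2.12, but the ordering of the three analyses holds throughout that range.

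Two further inferences fail. The d of 0.34 is not a product of an inefficient analysis: it follows from sample size, significance level and power alone, and only the conversion to points or percent depends on the SD. Nor do the documents show that pain is underpowered. One could multiply the uptake gap by the pilot fall, (0.61 − 0.24) × (7.3 − 6.0) = 0.48 points, and obtain 59% power for change against 76% adjusted. But that fall (D.1.1) was uncontrolled and measured at 6 months. The product also assumes no improvement without uptake, and D.2.12 itself allows for TAU uptake above 24%. The comparison is illustrative at most.

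Finally, these are secondary outcomes, and the reversed sentence alters no stated number. Both points stand and limit the weight of the finding.

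**Conclusion.** The point holds as one of specification and precision. The correlation sentence in D.2.12 is wrong in direction. E.2.10, D.2.11 and D.2.12 do not state one main pain contrast, and none specifies baseline adjustment. If the SD at each time is below the SD of change, as D.2.12 says, a change score is the least precise of the three natural choices. It needs 1.25 to 2.34 times the adjusted sample for 3-month SDs from just under 1.8 down to 1.2, and 1.46 times at 1.6.

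These figures rest on the plan's 1.6 and 1.8, two-sided 5% and complete data from all randomised participants. D.2.12 also says pain reduction is considered only in participants with BUP uptake. That sits badly with 135 per arm and with intention to treat, but it is a separate matter. No bias is shown. The change is worth making because it costs almost nothing.

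**What to change.** In E.2.10 and H3, name the 3-month difference between arms as the main pain estimand for BPI severity, BPI interference and PROPr. Estimate it either with the same scale's baseline as a covariate, or with a longitudinal model that has an arm-by-time term and arm means constrained equal at baseline. Changes from baseline can still be shown descriptively.

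In D.2.12, replace the explanation: with equal SDs, the SD of change exceeds the single-visit SD because the correlation is below 0.5. State the assumed 3-month SD. Beside the 0.61 points (8.4%) for change, give the adjusted detectable difference: about 0.51 points (7.0%) at a 3-month SD of 1.6, with 0.46 to 0.55 for SDs of 1.4 to just under 1.8, and about 0.55 (7.6%) at SD 1.6 if 84% are retained.

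The cost is wording only. The baseline scores are already scheduled, and neither the sample size nor the primary analysis changes.
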